The purpose of this study is to investigate the PD, PK, safety, tolerability, immunogenicity, and clinical efficacy of efgartigimod coformulated with recombinant human hyaluronidase PH20 (rHuPH20) as compared to efgartigimod IV infused in patients with gMG to evaluate the PD noninferiority of the SC formulation compared to the intravenous formulation. Study details include:

Study Duration: 12 weeks

Treatment Duration: 3 weeks

Health Measurements: Total levels of immunoglobulin G (IgG), levels of IgG subtypes, AChR-Ab levels, MG-ADL, QMG

Visit Frequency: Every week through visit 9, followed by a 2-week period between visit 9 and the end of the study visit

Number of Participants:

Approximately 110 participants will be enrolled and randomized in a 1:1 ratio to receive either efgartigimod PH20 SC or efgartigimod IV in addition to their concomitant gMG therapy. Approximately 110 participants are considered sufficient to allow better quantification of the safety and efficacy between the IV and SC routes of administration for efgartigimod. See also Section 9.2. Randomization will be stratified by Japanese versus non-Japanese participants. Within non-Japanese participants, randomization will be further stratified by AChR-Ab status. Up to 20% of participants included in the study will be AChR-Ab seronegative Japanese and up to 20% will be AChR-Ab seronegative non-Japanese patients.

Note: "Enrolled" means a participant, or their legally acceptable representative, has agreed to participate in a clinical study following completion of the informed consent process and screening. Potential participants screened to determine study eligibility but who do not participate in the study are not considered enrolled unless otherwise specified by the protocol. "Randomized" means that an enrolled participant has been randomly assigned to a treatment arm.

Intervention Groups and Duration:

The study duration is approximately 12 weeks, spanning the following study periods:

- screening period: approximately 2 weeks, with an additional 5 days allowed if needed to ensure AChR-Ab test results have been received
- treatment period: 3 weeks
- follow-up period: 7 weeks

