Note: All activities are performed predose on dosing days unless otherwise indicated. It is recommended to perform the MG-ADL scale prior to all other assessments.	predose	on dosing day	vs unless o	otherwise in	dicated. It i	is recommen	nded to peri	form the M(G-ADL sca	le prior to a	Il other asse	ssments.
^a After a participant completes the study and all EoS visit activities, the participant will be allowed, if eligibility criteria are met, to roll over into the open-label extension study ARGX-113-2002 to receive efgartigimod PH20 SC 1000 mg. ^b A UNS visit can occur at the request of the participant or the investigator. During the UNS visit, activities as indicated in the SoA can be performed at the discretion of the investigator. Because for the INS visit	study ar rtigimod lest of th	d all EoS visit PH20 SC 100 (e participant o	activities, 0 mg. or the inves	, the particij stigator. Du	pant will be ring the UN	e allowed, if VS visit, act	f eligibility ivities as in	criteria are dicated in t	met, to roll he SoA can	over into th t be perform	ie open-labe ned at the di	l extension study scretion of the

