9.3. Analysis Sets

The following analysis sets are defined:

Table 2:Analysis Sets

Analysis Sets	Description
Safety analysis set	All randomized participants who are exposed to the IMP
Intention-to-treat set	All randomized participants with a value for total IgG levels at baseline and at least 1 post-baseline timepoint
PK analysis set	Subset of safety analysis set with at least 1 postdose PK measurement

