9.4.1. General Considerations

- The baseline value will be defined as the last assessment prior to the first administration of efgartigimod.
- All study visits will be recalculated based on actual dates and will be referred to as "analysis visits," which will be used in the statistical analyses. The rules for calculating the analysis visits will be documented in the SAP. Rules for inputting partial dates or missing dates will also be documented in the SAP.

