9.4.2. Primary Endpoint

Definition of the Estimand for the Primary Endpoint

- Population: intention-to-treat (ITT) analysis set (see Table 2)
- Variable: Percent reduction from baseline in total IgG levels at day 29
- Main intercurrent events:
 - early treatment discontinuation for any reason prior to day 29
 - initiation of Ig therapy (IVIg and SCIg) as rescue therapy prior to day 29
 - missed doses

Handling of Main Intercurrent Events

For early treatment discontinuation or missed doses, the observation captured 7 days after the last dose will be used. If Ig therapy is used as rescue therapy prior to day 29, the last observation prior to the initiation of Ig therapy will be used.

Estimation of Treatment Effect and Statistical Inference

An analysis of covariance model (ANCOVA) will be used to estimate the mean percent reduction in total IgG levels from baseline at day 29 for each treatment arm, as well as the 2-sided 95% confidence interval for the difference between the 2 treatment arms. The model will include treatment as a factor and baseline total IgG level as a covariate.

When the upper limit of the 95% confidence interval (mean percent reduction with IV – mean percent reduction with SC) is below the margin of 10, the SC formulation will be considered noninferior to the IV formulation.

Complementary Analyses

To facilitate interpretation of the estimated treatment effect in the primary analysis, sensitivity analyses will be conducted where the main intercurrent events will be handled differently. Details will be provided in the SAP.

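### The Ig-rescue rule of the primary analysis sets no post-baseline floor and no precedence over the discontinuation rule, so a week-1 rescue can enter the day 29 ANCOVA as 0% reduction

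*Protocol*

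**What the plan says.** Protocol section 9.4.2 defines the primary variable as follows: "Variable: Percent reduction from baseline in total IgG levels at day 29". It lists "initiation of Ig therapy (IVIg and SCIg) as rescue therapy prior to day 29" as a main intercurrent event and states that in this case "the last observation prior to the initiation of Ig therapy will be used". For early treatment discontinuation or missed doses, the sentence before takes the observation made 7 days after the last dose. Sensitivity analyses that handle these events differently are promised, with details left to the SAP.

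Four other parts of the protocol determine what the rescue rule does:

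- **Baseline** (9.4.1): "The baseline value will be defined as the last assessment prior to the first administration of efgartigimod".
- **Sampling** (1.1 and 1.3): visits take place "Every week through visit 9, followed by a 2-week period between visit 9 and the end of the study visit", with PD samples on days 1, 8, 15, 22 and 29. On timing, "All activities are performed predose on dosing days unless otherwise indicated". The day 29 visit (V5) has a window of ±2 days. A PD sample at an unscheduled visit is optional.
- **ITT set** (9.3): "All randomized participants with a value for total IgG levels at baseline and at least 1 post-baseline timepoint".
- **Consequences of rescue** (6.8.3 and 7.1): use of a prohibited therapy ends study treatment, but the participant completes all remaining visits.

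**The concern.** The primary variable is meant to describe the IgG effect of four weekly doses. The rescue rule accepts any value taken before Ig, and nothing in it excludes the baseline value. If baseline is carried forward, the percent reduction is zero by construction. That number records when rescue happened and says nothing about the effect of either formulation.

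A 0% value lies far outside the expected distribution, so a single one shifts the arm mean and inflates the SD. In the IV arm it lowers the reference and helps a noninferiority claim. In the SC arm it works against a formulation that may truly be noninferior.

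Two further gaps concern samples taken after Ig. A rescued participant is also a discontinued one, and the discontinuation rule may select a sample that contains administered immunoglobulin. The words limiting the rule to rescue before day 29 also leave out Ig given on day 29 or 30 when the V5 sample is drawn later, up to day 31.

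**Working it through.** **1. The plan's own sample size.** Inputs from section 9.2: margin 10, IV mean 62, SC mean 60, SD 7.5 (alternatives 8.5 and 10), one-sided 2.5% two-sample t-test, 90% power. The exact noncentral-t calculation gives 20, 25 and 34 per arm. These match the stated 20 per arm and the totals of 50 and 68. With 13% attrition, 20/(1 − 0.13) = 23 per arm, or 46 in all. The plan's figures reproduce.

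**2. Value entered for rescue between dose 1 and the day 8 sample.**

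- Sampling is weekly and predose, so the last scheduled observation before Ig is the day 1 predose sample.
- Section 9.4.1 makes that sample the baseline.
- Percent reduction = 100 × (baseline − baseline)/baseline = 0.

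**3. Does the participant stay in the analysis?** Yes. Study treatment stops but visits continue (7.1), and the ITT set asks for one post-baseline IgG value without saying that it must precede rescue.

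**4. The two rules side by side, same participant.**

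| Rule in 9.4.2 | Value selected |
|---|---|
| Ig rescue: last observation before Ig | Day 1, i.e. baseline (0%) |
| Discontinuation: 7 days after last dose | About day 8, after Ig |

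Both apply, they disagree, and no order is given.

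**5. Size of one 0% value.** About 110 participants randomized 1:1 gives 55 per arm.

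- SC arm: 60/55 = 1.09 points. IV arm: 62/55 = 1.13 points. Each is about 11% of the margin.
- Distance from the SC mean: 60/7.5 = 8 SD, or 60/10 = 6 SD.
- Effect on SD: one zero adds about 60²/55 = 65 to the SC arm variance. The pooled SD rises from 7.5 to about 9.4, or from 10 to about 11.5.

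**6. Effect on the test.** Simulation of the two-sample t-test (upper 97.5% limit below 10), 55 per arm, at least 40,000 trials per case, no baseline covariate. The numbers of cases are assumptions.

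| Cases entered as 0% | False claim at true difference 10 | Power at difference 2, SD 7.5 | Power at difference 2, SD 10 |
|---|---|---|---|
| None | 2.5% | >99.9% | 98.6% |
| One, IV only | about 4.5% | >99.9% | 99% |
| Two, IV only | about 9% | >99.9% | >99% |
| One, SC only | below 0.5% | 99% | 91% |
| Two, SC only | below 0.1% | 89% | 70% |
| One in each arm | 0.3% (SD 7.5), 0.9% (SD 10) | 99.7% | 95% |

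**7. One-dose values (rescue between the day 8 and day 15 samples).** The protocol gives no one-dose reduction, so 20% to 40% is assumed. Each SC case shifts the mean by (60 − 40)/55 = 0.36 to (60 − 20)/55 = 0.73 points. With two SC cases power is 98% to over 99% at SD 7.5 and 88% to 96% at SD 10. With one IV case the false-claim rate is 3.7% to 4.6%.

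**The case against.** **The 0% is not inevitable.** Rescue requires clinical deterioration (6.8.3), which is a natural occasion for an unscheduled visit with a PD sample. The discontinuation rule can also be read as governing. A reader might infer that every week-1 rescue is exactly 0%; the protocol supports this only when no unscheduled sample exists and the rescue rule is the one applied. What stands is that the text permits 0%, and that the competing rule selects a post-Ig sample instead.

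**The effect has no fixed direction.** A reader might infer a bias towards noninferiority. That follows only if the cases fall in the IV arm. Cases in the SC arm count against the claim, and one in each arm makes the test conservative.

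**The arm size matters.** A reader might deduct 13% attrition and work with 48 per arm, where two SC cases bring power down to about 73%. Section 7.1 keeps discontinued participants in follow-up and the ITT set keeps them in the analysis, so about 55 is the better figure.

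**Using a value from before rescue is a legitimate choice.** One-dose values follow from a prespecified rule of that kind, and their effect on power is small at SD 7.5. A reader might infer that the primary analysis should become a mixed model for repeated measures (MMRM) on pre-Ig values. That would exchange the stated rule for a hypothetical estimand. It would also treat participants who stopped dosing as if they had continued, which is a debatable trade-off and not the correction of an error.

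**Day 29 may simply mean V5.** Section 9.4.1 leaves the mapping of visits to the SAP. That softens the point about Ig on day 29 or 30, but the event as worded still ends at day 29 while the sample may come later.

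**Sensitivity analyses are promised.** They help interpretation but do not change the result that decides noninferiority.

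**Conclusion.** The point holds as a defect in a stated rule. Section 9.4.2 allows baseline to serve as the day 29 outcome, does not rank two rules that both apply to a rescued participant, and leaves out Ig given between day 29 and a late V5 sample.

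Each 0% value moves an arm mean by about 1.1 points. One or two cases confined to the IV arm raise the false-claim rate from 2.5% to about 4.5% or 9%. Two confined to the SC arm lower power to 89% at SD 7.5 or 70% at SD 10.

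These figures rest on assumed case counts, 55 per arm and a t-test without the baseline covariate. The protocol gives no rescue rate, and with few or no week-1 rescues the conclusion of the trial is unlikely to change. The finding does not show that the primary analysis is invalid or needs another model. It supports a narrow repair, which is worth making because it costs almost nothing.

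**What to change.** In section 9.4.2, with matching text in the SAP:

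1. State that only a post-baseline IgG value taken before Ig may stand in for day 29, and that baseline is never an outcome value. If no such value exists, treat day 29 as missing and multiply impute it by arm before the stated ANCOVA.
2. State that the Ig-rescue rule takes precedence over the discontinuation and missed-dose rule, so that no sample taken after Ig is used.
3. Define the event as Ig started before the IgG sample used for day 29, in place of before day 29.
4. Add, as one of the promised sensitivity analyses, an analysis that sets all post-Ig values to missing and uses the weekly values (MMRM or multiple imputation). Keep the primary analysis otherwise as it is.

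The cost is a few lines of wording and standard programming on data already collected. The downside is an imputation assumption for the very few participants who have no post-baseline value before Ig. No clinical rule changes.

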 - In the AChR-Ab seropositive population, the maximum mean percent change from baseline in total IgG levels was approximately 61% 1 week after the last infusion of a treatment cycle. No substantial mean percent change in total IgG levels from baseline was observed in the placebo arm. The results were comparable between AChR-Ab seropositive participants and the overall population.
 - Efgartigimod IV 10 mg/kg q7d was safe and well tolerated. The efgartigimod IV arm had a lower percentage of participants reporting TEAEs than the placebo arm. The majority of TEAEs reported were mild or moderate in severity.

2.3.3. rHuPH20 Risk Assessment

More information on the use of rHuPH20 (brand name Hylenex) is available in the rHuPH20 IB^5 .

SC injections were well tolerated in healthy subjects, dehydrated pediatric patients, hospice and palliative care patients, patients with type 1 and 2 diabetes, and patients with rheumatoid arthritis. SC injections of rHuPH20 alone or in combination with lactated Ringer's solution, normal saline, co-injected drugs (eg, morphine, ceftriaxone, ondansetron), peptides (eg, insulin and insulin analogs), or proteins (IgG and adalimumab) have been well tolerated in all clinical studies.

Most AEs observed were mild, transient injection site reactions, including erythema, pain, bruising, pruritus, burning, tenderness, edema, induration, irritation, paresthesia, numbness, and rash. Moderate injection site reactions, which occurred less frequently, include burning, erythema, pain, and numbness. Mild-to-moderate headache was also reported.

Hylenex prescribing information as of February 2016 contains the following warnings and precautions:

- rHuPH20 should not be injected into or around an infected or acutely inflamed area because of the danger of spreading a localized infection. rHuPH20 should not be used to reduce the swelling of bites or stings.
- rHuPH20 should not be applied directly to the cornea. It is not for topical use.

2.3.4. rHuPH20 Benefit Assessment

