6.3. Measures to Minimize Bias: Randomization and Blinding

• This is an open-label study; potential selection bias will be reduced by central randomization.

- Participants will be assigned a unique patient identification number at screening. Upon randomization, the participant will be assigned to a treatment arm according to the randomization schedule generated prior to the start of the study.
- Randomization will be stratified by Japanese versus non-Japanese participants. Within the non-Japanese participants, randomization will be further stratified by AChR-Ab status.

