9. STATISTICAL CONSIDERATIONS

The statistical analysis will be performed by the sponsor's designated CRO using statistical analysis systems (SAS) software (SAS Institute, Cary, NC, United States) version 9.4 or higher, and the software package R, if applicable. The standard operating procedures (SOPs) and work instructions of the sponsor's designated CRO will be used as the default methodology if not otherwise specified.

A detailed and comprehensive Statistical Analysis Plan (SAP) will be written and signed-off prior to final analysis database lock. Minor changes to the statistical methods set out in this protocol do not require a protocol amendment but will be documented (as changes from the protocol) in the SAP and in the clinical study report(s). The below sections contain the main general features of the statistical analysis. More details will be provided in the SAP.

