IgG= immunoglobulin G; IV=intravenous(ly); MG-ADL=Myasthenia Gravis Activities of Daily Living; mITT=modified intention-to-treat

Note: To minimize potential modeling bias introduced by outlier data points, only week 1 to week 6 data from all cycles in study ARGX-113-1704 were included.

Based on data from the phase 3 study ARGX-113-1704, the mean percent decrease in total IgG levels with the IV formulation is expected to be approximately 62 (standard deviation 7.5). Assuming the total IgG percent reduction from baseline with the SC formulation is 60 (2 less compared to the IV formulation) along with a standard deviation of 7.5, 20 participants per treatment arm are needed to reach 90% power to detect noninferiority using a 1-sided 2-sample t-test at a 2.5% level of significance. To account for participant discontinuation, 3 additional participants per treatment arm have been added. A sample size of 46 participants will need to be enrolled and randomized, allowing for a 13% attrition rate.

Clinical Study Protocol ARGX-113-2001 v2.0 Efgartigimod IV and SC

The assumptions utilized in the sample size calculations will be evaluated in study ARGX-113-1907, which will compare the PD, PK, safety, and tolerability of multiple doses of efgartigimod PH20 SC and efgartigimod IV in healthy participants. Study ARGX-113-1907 will use the same dosage as in the current study and will provide a detailed assessment of the PD effect in healthy participants, which is expected to represent the effect in participants with gMG. If the results of study ARGX-113-1907 indicate that the pooled standard deviation of the mean percent decrease in total IgG levels is larger than 7.5, the sample size will be adapted accordingly. If the pooled standard deviation is:

- 8.5, then a total of 50 participants will be recruited, with 6 additional participants added to account for discontinuations for a total of 56 participants (based on a pooled standard deviation of 8.5)
- 10.0, then a total of 68 participants will be recruited, with 8 additional participants added to account for discontinuations for a total of 76 participants (based on a pooled standard deviation of 10)

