Seventy-six participants would suffice for the noninferiority comparison between SC and IV based on IgG reduction at day 29; however, increasing the sample size to approximately 110 participants will provide better quantification of the clinical safety and efficacy profile of the SC formulation in patients with gMG while the IV formulation will serve as a reference treatment in this randomized study.

Note: "Enrolled" means a participant's, or their legally acceptable representative's, agreement to participate in a clinical study following completion of the informed consent process and screening. Potential participants who are screened to determine eligibility for the study, but do not participate in the study, are not considered enrolled unless otherwise specified by the protocol. "Randomized" means that an enrolled participant has been randomly assigned to a treatment arm.

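### The primary ANCOVA leaves out the three randomization strata: if strata differ in IgG reduction, the noninferiority interval is slightly wider than it need be, in the conservative direction

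*Protocol*

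**What the plan says.** Section 6.3 of the protocol sets out the allocation scheme: "Randomization will be stratified by Japanese versus non-Japanese participants. Within the non-Japanese participants, randomization will be further stratified by AChR-Ab status". The synopsis and Section 4.1 say the same. AChR-Ab status is a stratifier only among non-Japanese participants, so there are three strata: Japanese, non-Japanese seropositive and non-Japanese seronegative.

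Section 9.4.2 names the terms of the primary model: "The model will include treatment as a factor and baseline total IgG level as a covariate". Noninferiority is declared when the upper limit of the two-sided 95% interval for IV minus SC, taken from that model, is below 10. The stratum does not appear there or elsewhere in Section 9, and no reason is given for leaving it out.

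On whether strata might differ, Section 2.3.2 says of total IgG in the earlier phase 3 IV study: "The results were comparable between AChR-Ab seropositive participants and the overall population". The protocol gives no IgG reduction by Japanese status.

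**The concern.** When allocation is balanced within strata, differences between strata largely cancel out of the treatment contrast. A model without the strata still counts those differences as residual noise. Its standard error is then larger than the true sampling variability of the estimate, the interval is too wide, and the one-sided error falls below the nominal 2.5%.

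Both the noninferiority decision and the reported IV–SC difference come from this one interval. What is at stake is some precision in it. The direction is safe: the omission makes noninferiority slightly harder to show.

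**Working it through.** **Inputs from the protocol.** Margin 10, one-sided 2.5%, expected means 62 (IV) and 60 (SC), SD 7.5 with fallback values 8.5 and 10 (Sections 9.1 and 9.2); about 110 participants, 1:1 (synopsis); up to 20% seronegative (Section 4.1).

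**Assumptions.** Japanese share 10%. With 20% of the remaining 90% seronegative, the shares are 10/72/18%. Stratum shifts are assumed and must be read as what remains after adjustment for baseline IgG. Allocation is in permuted blocks of 4 within stratum; the protocol does not state a block scheme.

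**1. The plan's own sample size.** The normal approximation is n per arm = 2·SD²·(1.960 + 1.282)²/(10 − 2)², which gives 19, 24 and 33 for SD 7.5, 8.5 and 10. The noncentral t calculation, which matches the t-test in Section 9.2, gives 20, 25 and 34 (power 0.908, 0.903, 0.902). Totals are 40, 50 and 68, or 46, 56 and 76 with the stated allowances for discontinuation. The protocol's figures are reproduced.

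**2. Width ratio in closed form.** Let p be the stratum shares and d the shifts relative to non-Japanese seropositive participants. The between-stratum variance is V = Σp·d² − (Σp·d)². With within-stratum SD s, the interval without strata is wider by a factor of about √(1 + V/s²). At s = 7.5, s² = 56.25.

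| Shift: Japanese / non-Japanese seronegative | V | Ratio | Simulated width without / with strata |
|---|---|---|---|
| 0 / 0 | 0 | 1.000 | 5.69 / 5.69 |
| 2.5 / 2.5 | 1.75 − 0.49 = 1.26 | 1.011 | 5.75 / 5.69 |
| 0 / 5 | 4.50 − 0.81 = 3.69 | 1.032 | 5.87 / 5.69 |
| 5 / 5 | 7.00 − 1.96 = 5.04 | 1.044 | 5.93 / 5.68 |
| 5 / −5 | 7.00 − 0.16 = 6.84 | 1.059 | 6.02 / 5.69 |

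The simulated widths are from 8000 trials per row at N = 110. The extra width on each side is (5.93 − 5.68)/2 ≈ 0.12 points for the 5 / 5 row and (6.02 − 5.69)/2 ≈ 0.17 points for the 5 / −5 row.

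**3. Other readings of the SD.** If 7.5 is the total SD, the within-stratum variance is 56.25 − V. The ratios become √(56.25/51.21) = 1.048 for 5 / 5 and √(56.25/49.41) = 1.067 for 5 / −5. At SD 10 the 5-point cases range from √(1 + 5.04/100) = 1.025 to √(100/93.16) = 1.036.

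**4. What a large effect would need.** At the same shares and SD 7.5, shifts of 10 / 8 give V = 21.52 − 5.95 = 15.57 and a ratio of 1.13. Shifts of 8 / −10 give V = 24.40 − 1.00 = 23.40 and a ratio of 1.19. These shifts are about as large as the margin. A separate simulation with the two serostatus strata 10 points apart and the Japanese stratum midway gave 13% (6.41 / 5.68). With a 3-point difference for the Japanese stratum alone it gave 0.7%.

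**5. One-sided error at a true difference of 10.** Without strata it was 0.0216 (5 / 5) and 0.0201 (5 / −5); with strata, 0.0264 and 0.0254. The Monte Carlo standard error is √(0.025 × 0.975/8000) ≈ 0.0017, so the values with strata agree with the nominal 0.025. In the case 10 points apart, the mean model standard error was 1.62 against a true SD of the estimate of 1.45, and the error without strata was 0.012. No scenario showed inflation.

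**6. Power at a true difference of 2, N = 110.** At within-stratum SD 7.5 it was 0.9995 without and 0.9996 with strata (5 / 5), and 0.9999 either way (5 / −5). At SD 10 it was 0.9841 / 0.9860 and 0.9816 / 0.9839. Reading 10 as the total SD gives 0.9875 / 0.9893 and 0.9864 / 0.9893. The largest loss is 0.3 percentage points.

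**The case against.** The strongest reply is that nothing here is invalid. A baseline-adjusted ANCOVA under 1:1 randomization gives a sound comparison, the loss depends on a stratum effect the protocol does not show, and no decision changes. Section 2.3.2 points to little effect of serostatus, and blocking FcRn lowers all IgG subtypes whatever the antibody status. Section 9.2 says of the primary comparison: "Seventy-six participants would suffice for the noninferiority comparison between SC and IV based on IgG reduction at day 29", and about 110 are planned. Most of this stands, and it is why the point ranks low. Two limits apply. The serostatus evidence is indirect, because the overall population contains the seropositive patients, and there is no evidence at all on Japanese status.

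A second reply is that model details belong in the SAP, which I have not seen and which may already include the stratum. But Section 9.4.2 does not leave the terms open. It names them, and defers only the sensitivity analyses to the SAP. Adding the stratum would be a change from the protocol.

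A third reply is that the conservative error rate depends on balance within strata, which the protocol does not describe beyond calling the randomization stratified. That is right. Without such balance the error of the model without strata is close to nominal, and still not inflated.

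**Conclusion.** The concern holds as a minor point of precision. The protocol stratifies randomization on three groups and fixes a primary model that ignores them, without a reason. For stratum shifts up to 5 points the cost is an interval 0 to 7% wider at SD 7.5 and up to 4% wider at SD 10. Larger losses need shifts of about the size of the margin, which nothing in the protocol supports. These figures assume shares of 10/72/18%, the stated shifts and balanced allocation within strata. The omission does not raise type I error, the sample size needs no change, and the noninferiority conclusion is hardly at risk.

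**What to change.** In Section 9.4.2, specify the primary ANCOVA as treatment, three-level randomization stratum and baseline total IgG. If the sponsor prefers the model without the stratum, the reason should be written down, although that does not recover the precision.

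The cost is one line of text and two residual degrees of freedom (110 − 3 = 107 becomes 110 − 5 = 105). With no stratum effect the interval width is unchanged. No new data are needed, since the stratum is recorded at randomization. Section 9 gives a route through the SAP: "Minor changes to the statistical methods set out in this protocol do not require a protocol amendment". The change should be documented there as a departure from the protocol and fixed before database lock, so that the choice between the two models cannot depend on the results of this open-label trial.
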